#### 3.3. Discussion of Subject Population

There is no known effective antiarrhythmic treatment in ARVC patients. Flecainide is a promising option, but there are no clinical trials to prove its efficacy and safety in these patients. The proposed pilot study to assess the effect of flecainide on cardiac arrhythmias detected by long-term ECG monitoring will provide preliminary data. Assessing safety of this therapy is of major importance in view of the results of the CAST trial that showed increased mortality in patients with ischemic heart disease after myocardial infarction treated with antiarrhythmic drugs including flecainide (Echt et al. 1991). To assure the safety of subjects the study is including only ARVC patients with ICDs and excluding patients with significant left ventricular dysfunction and significant heart failure, who constitute a small minority of ARVC patients.

# 4. SUBJECT IDENTIFICATION, RECRUITMENT AND CONSENT

#### 4.1. Method of Subject Identification and Recruitment

[figure not shown]
Subjects will be recruited from US enrolling centers.

#### 4.2. Process of Consent

The site investigator and/or study coordinator will consent subjects in this study. The consent document will be used as a guide for the verbal explanation of the study and will be the basis for a meaningful exchange between the investigator and the potential subject. The subject's signature provides documentation of agreement to participate in a study, but is only one part of the consent process. The consent document will not serve as a substitute for discussion and the potential subject will be invited to ask any questions or concerns that will be answered by the study team members. Once a participant indicates that he or she does not want to take part in the research study, this process stops. The potential subject will be given sufficient opportunity to consider whether or not to participate. Refusal to take part or withdraw from the study at any time will not interfere with the future medical treatment of the potential subject.

## 5. METHODS AND PROCEDURES

This is a randomized double-blinded placebo-controlled crossover trial on the effect of flecainide on the frequency of ventricular arrhythmias of 38 ARVC patients. The crossover design shown below requires a 10-week treatment with each patient receiving flecainide 100 mg bid for 28 days and placebo for 28 days in a blinded randomized order. The Figure 4 and Table 2 below show the study design and the schedule of activities.

#### Table 2. Schedule of Activities.

	Visit	Visit	Visit 2	Visit	Visit	Visit	Visit	Visit	Visit	Visit	Visit
	0 a Screen	1 a Ran- domize	Drug Initia- tion	3	4	5	6 Second Drug Bottle	7	8	9	10 Close- out
Start Medication Weeks	-4-0 weeks	-4-0 weeks	0	1 week + 2 days	3 weeks + 2 days	4 weeks + 2 days	5 weeks + 2 days	6 weeks + 2 days	8 weeks + 2 days	9 weeks + 2 days	10 weeks + 2 days
In person visit	Yes in clinic	No	No By phone	No by phone	In home or in clinic d	No by phone	No by phone	No by phone	In home or in clinic d	No by phone	No by phone
Study Periods			Period	1			Period 2	2			
Informed Consent	√										
Pregnancy Test b	√										
Medical History	√										
Holter Monitor c	✓										
ECG	✓				✓				✓		
Randomization		✓									
Blood Sample					√				✓		
7-day ECG Monitor					√				✓		
Remote ICD interrogation				√				✓			✓
Adverse event				✓	√	✓	√	✓	✓	√	✓
Drug Dispense/Accountability			~				~			~	
Stop and return study drug and ZIO-Patch						~				~	
Study Closeout											✓

a - Visits 0 and 1 could be done on the same day.

b - Pregnancy test must be obtained prior to randomization

c – Holter Monitor for subjects have had a washout of antiarrhythmic therapy

d - Visit at home will be done by specialized services with: ECG recording and blood draw; ZIO-Patch could be self-applied by

subject or by study staff member. These visits could take place in a clinic if this is what subject and investigator are agreeable to.

# 5.1. Visits

## 5.1.1. Visit 0: Subject Screening and Consent

Each potential subject will have inclusion and exclusion criteria verified by study personnel prior to approaching a potential subject for consent. The consent process begins with the protocol described to them by one of the physicians or research coordinators at the enrolling site. Potential subjects will sit down with the coordinator or physician and have the opportunity to ask questions. Those who meet inclusion/exclusion criteria will then be asked to sign consent for study participation. At this time they will sign an "informed consent" form that is fully approved by the local IRB following local IRB consent administration regulations. It is the responsibility of the investigator to ensure that subjects are eligible to participate in the study prior to enrollment and throughout the study. Once informed consent has been obtained, all screening tests and procedures have been assessed and study eligibility has been confirmed, subjects will be assigned a unique subject identification number. The enrolling site will enter data in the web base system and the system will assign the subject ID after study eligibility criteria are met. The scheme for assigning subject ID is as follow: first 2 numbers are assigned for enrolling site and will not change for duration of the study. Next two numbers are specific to a randomized subject in the enrolling site.

The principal investigator ensures that informed consent from each potential research participant will be obtained by an IRB approved consent designee and documented. The following persons may obtain consent: the principal investigator, sub-investigators, or study team members listed on the IRB application form as a consent designee. Each individual who will interact with potential research participants to obtain consent will submit evidence of human subject compliance training per local IRB regulations.

After written informed consent is obtained, a medical history and an ECG will be obtained from the subject. Any woman of childbearing age must have a negative pregnancy urine or blood test prior randomization, unless the woman is surgically sterile or post-menopausal (no menstrual periods for more than one year). Investigators will verify that subjects must use a medically acceptable method of birth control prior to study entry and while participating in the study.

Subjects are expected to be on one of the following beta-blockers unless contraindicated: metoprolol, propranolol, atenolol, nadolol, carvedilol or bisoprolol. Subjects on antiarrhythmic medications including: sotalol, mexilitene, flecainide, quinidine, procainamide, propafenone, disopyramide, dronedarone, or phenytoin will require washout lasting a minimum of 5 days and a subsequent 24-hour Holter recording demonstrating at least 500 VPBs prior to being considered for randomization. Study sites are provided with dedicated Holter recorders to be used if needed. Patients should return Holter recorders in person or by mail to the enrolling site personnel who will upload Holter files into the University of Rochester Box.com system for analysis. Enrolling centers will be informed about the results of 24-hour Holter analysis within 2 business days. Subjects not meeting eligibility criteria of at least 500 VPBs in 24-hour Holter after washout of medication used prior to the study drug initiation will be withdrawn and replaced.

# 5.1.2. Visit 1: Randomization (Visit 1 could take place on the same day as Visit 0):

During this study visit:

- Study personnel will confirm subject's eligibility if not possible during Visit 0. No patient contact is needed if subject remains eligible.
- Study personnel will randomize subject via computer entry of the study data which will trigger the University of Rochester IDS to ship study drug, diary, ZIO-Patch with instructions, blood drawing kit, and prepaid return envelope for next day delivery via Federal Express to subject. The Zio-Patch is identified only by a serial number and will be sent to the manufacturer to retrieve information regarding ECG findings.
- For subjects requiring a 24-hour Holter recording after washout from antiarrhythmic medication, eligibility will need to be reconfirmed based on number of VPBs found on holter monitoring
- If subject is found to have less than 500 VPBs in 24-hour Holter, the subject will be informed that he/she will be withdrawn from the study.

# **5.1.3. Visit 2: Phone Visit** (within 7 days from Visit 1)

The following tasks will be performed and documented at the Visit 2:

- Enrolling site staff member will confirm receipt of study shipment and review contents with subject.
- Review study drug prescribing regimen, diary and emphasize importance of compliance with subject. Instruct patient to begin taking study drug and record the date of the subject's first dose of study medication.

# 5.1.4. Visit 3: Phone visit (One week after initiating study drug)

During this follow-up visit:

• An ICD interrogation (with a manual transmission by patient, if system is not automatic) from remote device monitoring system should be obtained.

- Study drug prescribing regimen, diary and importance of compliance will be reviewed with subject.
- Adverse events will be assessed and reported.
- **5.1.5. Visit 4**: **In person visit in home or in clinic** (Three weeks after initiating study drug) During this follow-up visit:
  - A standard 12-lead ECG recording will be performed.
  - Blood sample will be drawn for flecainide levels. A teaspoon (5ml) of blood is needed for this sample. This blood sample will be sent to a specialized lab. Paper copy of ECG will be uploaded to the Box.com at the University of Rochester.
  - A ZIO-Patch (a small, adhesive, water-resistant one lead ECG recorder) will be applied to the chest for a continuous 24-hour monitoring over 7 days. ZIO-Patch could be self-applied or applied by study staff member. At the end of the 7 days the patch must be removed and returned to the University of Rochester
  - Review study drug prescribing regimen, diary and importance of compliance will be reviewed with subject.
  - Adverse events will be assessed and reported.

# **5.1.6. Visit 5**: **Phone visit** (Four weeks after initiating study drug)

During this follow-up visit study:

- Patient will be reminded to:
  - stop study drug from first bottle (begin wash out period)
  - remove ZIO-Patch
  - return the medication bottle, diary and ZIO-Patch in a pre-paid mailer to the University of Rochester.
- Adverse events will be assessed and reported.

# 5.1.7. Visit 6: Phone visit (Five weeks after initiating study drug)

During this follow-up visit:

- Enrolling site will confirm receipt of study shipment and review contents with the subjects. Shipment will include: second bottle of study drug, diary, Zio-Patch with instructions, blood drawing kit and prepaid return envelope for next day delivery via Federal Express.
- Study drug prescribing regimen, diary and importance of compliance will be reviewed with subject.
- Instruct patient to begin taking study drug and record the date of the subject's first dose of study medication from second bottle. Adverse events will be assessed and reported.

# **5.1.8. Visit 7**: **Phone visit** (Six weeks after initiating study drug)

During this follow-up visit:

- An ICD interrogation (with a manual transmission by patient, if system is not automatic) from remote device monitoring system will be obtained.
- Study drug prescribing regimen, diary and importance of compliance will be reviewed with subject.
- Adverse events will be assessed and reported.
- **5.1.9. Visit 8**: In person visit in home or in clinic home visit (Eight weeks after initiating study drug)

During this follow-up visit:

- A standard 12-lead ECG recording will be performed.
- Blood sample will be drawn for flecainide levels. A teaspoon (5ml) of blood is needed for

this sample. This sample will be sent to a specialized lab for analysis and paper copy of ECG will be sent to the University of Rochester.

- A ZIO-Patch (a small, adhesive, water-resistant one lead ECG recorder) will be applied to the chest for a continuous 24-hour monitoring over 7 days. ZIO-Patch could be selfapplied or applied by study staff member. At the end of the 7 days the patch must be removed and returned to the University of Rochester
- Study drug prescribing regimen, diary and importance of compliance will be reviewed with subject.
- Adverse events will be assessed and reported.

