# **5.1.10. Visit 9**: **Phone visit** (Nine weeks after initiating study drug)

During this follow-up visit study:

- Patient will be reminded to:
  - stop study drug from second bottle
  - remove ZIO-Patch
  - return the medication bottle, diary and ZIO-Patch in a pre-paid mailer to the University of Rochester.
- Adverse events will be assessed and reported.

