## 5.2. Treatment Dosage and Administration

Each subject will take 1 blinded capsule of study drug (flecainide or a placebo) dose BID per randomization scheme for 28 days. After 28 days there will be a 7-day washout period. At the end of the washout period, each subject will then take 1 blinded capsule of study drug (flecainide or placebo) for the next 28 days.

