## 5.4. Safety Assessments

The assessments that will be performed to evaluate safety include medical history, standard 12-lead ECG, implanted device interrogation and the use of the 7-day ZIO-Patch monitor and will be quantified by:

a) VPBs on 7-day ECG monitoring to determine the possibility of proarrhythmia defined as a 3-fold increase in number of VPBs;

b) Total burden of nun-sustained and sustained (ICD treated and untreated) VT episodes on interrogation of ICDs evaluated after the first week and after the fourth week of study drug administration with a 5-fold increase in number of VT episodes defining proarrhythmia.

c) QRS prolongation on ECG defined as >40ms in comparison to baseline and the new presence of the Brugada pattern of the ECG. We expect 17-29% prolongation of the QRS but prolongation >30% (40ms) will be unusual. The appearance of cove-type Brugada pattern will be monitored.

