# 8. STUDY DRUG ADMINISTRATION/ASSIGNMENT

## 8.1. Study Drug

This study is IND exempt per FDA; meeting the criteria set forth in 21 CFR 312.2(b) and 320.31(b). The University of Rochester Investigational Drug Service (IDS) will prepare and dispense the study medication. All capsules of study drug will be identical in appearance (same size and color). Blinded capsules will be prepared via over-encapsulation. Active doses will

consist of 2 x 50 mg flecainide tablets placed inside larger opaque colored capsules and backfilled with lactose. Placebo doses will consist of the same opaque colored capsules filled with inert powder (lactose). Study subjects will be instructed to swallow all capsules whole and not to open them. Each subject will be dispensed 56 blinded doses per treatment period, per randomization (2 doses/day x 28 days = 56 doses per period). The University of Rochester Investigational Drug Service (IDS) will receive the subject randomization assignment and prepare and ship study drug directly to the subject for next day delivery via Federal Express. At the time of crossover and at the study closeout, bottles will be collected for study drug accountability. Subjects will be provided a pre-paid mailer to return unused study drug to the University of Rochester IDS.

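### Period 2 visits are timed from the first bottle-1 dose, not from the recorded bottle-2 start, so the one-week ICD check and the patch align less closely with treatment than in Period 1; a small, cheap fix

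*Combined protocol and SAP*

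**What the plan says.** Table 2 counts every visit in weeks from Visit 2, when bottle 1 is started, and gives each later visit a window of 2 days either side. Visit 6 is at 5 weeks. At that call (section 5.1.7) the site is to "Instruct patient to begin taking study drug and record the date of the subject's first dose of study medication from second bottle".

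The headings of the later visits keep the original clock. Visit 7, with the ICD interrogation, is "Six weeks after initiating study drug" (5.1.8). Visit 8, when the patch goes on, is "Eight weeks after initiating study drug" (5.1.9). At Visit 9 (5.1.10), at nine weeks, one call reminds the patient to "stop study drug from second bottle" and to take the patch off; Visit 5 does the same in Period 1. Since Visit 6 is itself five weeks on this clock, its origin can only be the first bottle-1 dose.

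Three other statements bear on the point:
- Section 5.4 wants VT episodes on ICD interrogation "evaluated after the first week and after the fourth week of study drug administration", and 14.3 makes these interrogations part of the DSMB's main focus for each treatment.
- Section 8.1 fixes the supply: "2 doses/day x 28 days = 56 doses per period".
- Section 5.2 says: "After 28 days there will be a 7-day washout period".

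**The concern.** A crossover compares a patient's two periods, so both should be measured at the same points of exposure. In Period 1 the clock starts with the drug, and only the visit's own window separates nominal from actual exposure. In Period 2 two windows add up: that of the Visit 6 call, which starts bottle 2, and that of the later visit, which takes no account of when bottle 2 started. A site can follow Table 2 exactly and still interrogate the ICD after 3 days on the second treatment, or record patch days after the last capsule.

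Two things are affected. One is the early ICD safety check, whose on-drug exposure varies more in Period 2. The other is the 7-day recording that supplies the primary VPB outcome: off-drug days in it dilute the treatment contrast when flecainide is the second treatment.

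**Working it through.** **Inputs.** Day 0 is the first bottle-1 dose. From Table 2, each within 2 days: Visit 3 on days 5-9, Visit 4 on 19-23, Visit 5 on 26-30, Visit 6 on 33-37, Visit 7 on 40-44, Visit 8 on 54-58, Visit 9 on 61-65, Visit 10 on 68-72. The patch is worn for 7 days (5.1.5, 5.1.9).

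**The plan's own figures.** 2 doses × 28 days = 56 doses, as section 8.1 states. Nominally 28 + 7 + 28 = day 63, which is week 9 and matches Visit 9. At nominal times the ICD check is at 42 − 35 = 7 days on bottle 2, and the patch ends on day 56 + 7 = 63, with the supply. The nominal schedule is consistent.

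**Extremes for the ICD check.**
- Period 1: Visit 3 at 5-9 days on drug.
- Period 2: earliest 40 − 37 = 3 days, latest 44 − 33 = 11 days.

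**Extremes for the patch** (every capsule taken on time).
- Period 1: the patch ends on days 26-30 and the supply on day 28, so overrun is at most 30 − 28 = 2 days.
- Period 2: the patch ends on days 61-65 (54-58 plus 7) and the supply on days 61-65 (33-37 plus 28), so overrun is at most 65 − 61 = 4 days. Visit 9 may be as late as day 65, so it need not cut this short.

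**How often.** The documents do not say how visits spread over their windows. I assume each visit is uniform over its five days and independent of the others.

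*ICD check.* Visit 7 minus Visit 6 has 25 equally likely combinations. Outside 5-9 days: 2 × (2 + 1)/25 = 6/25 = 24%. The SD is √(2 + 2) = 2.0 days, against √2 = 1.4 in Period 1. Before day 7: (1 + 2 + 3 + 4)/25 = 10/25 = 40% in Period 2, and 2/5 = 40% in Period 1.

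*Patch, with the Visit 5 or Visit 9 call ending the recording if it comes before the seventh day of wear.* Overrun is the positive part of min(patch end, call) − supply end.
- Period 1 (25 combinations): 1 day in 3 and 2 days in 1; mean (3 × 1 + 1 × 2)/25 = 0.2 days.
- Period 2 (125 combinations): 1 day in 16, 2 in 9, 3 in 4 and 4 in 1; mean (16 + 18 + 12 + 4)/125 = 50/125 = 0.4 days. More than 2 days: 5/125 = 4%. Four days: 1/125 = 0.8%.

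*Patch, with the call ignored* (recording always runs 7 days and drug runs to the end of supply).
- Period 1: mean (1 + 2)/5 = 0.6 days.
- Period 2: mean (4×1 + 3×2 + 2×3 + 1×4)/25 = 0.8 days. More than 2 days: 3/25 = 12%. Four days: 1/25 = 4%.

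**Dilution.** Take the 40% reduction from section 14.1 and let the effect stop with the last capsule, which is the worst case. The reduction shown is 0.40 × (1 − off-drug days/7).
- Call ignored: 0.40 × (1 − 0.8/7) = 35.4% in Period 2 and 0.40 × (1 − 0.6/7) = 36.6% in Period 1.
- Call ends recording: 37.7% and 38.9%. Dividing by 7 is approximate here, because an early call also shortens the recording.
- The gap is 0.40 × 0.2/7 = 0.011 either way, about 1.1 points. With half the patients given flecainide second, the pooled estimate moves by about 0.6 points. If the effect lasts through the recording, the gap is zero.

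**After re-anchoring.** Visit 7 at bottle-2 start plus 7 ± 2 gives 5-9 days. The patch applied at start plus 21 ± 2 ends at start plus 26-30, against supply end at start plus 28, so overrun is at most 2 days. Both match Period 1. Checks before day 7 stay at 40%.

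**The case against.** The strongest objection is that section 5.2 already sets the dosing rule, 28 days on, 7 off, 28 on, which puts bottle 2 at day 35. On that reading the ICD check is at 5-9 days, the overrun is at most 2 days, and both differences vanish. The reading is possible, but it does not settle the matter. Table 2 gives Visit 6 its own window, and 5.1.7 ties the start to that call. Stopping bottle 1 at the Visit 5 call (days 26-30) and waiting 7 days also gives days 33-37.

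Second, the Visit 9 call tells the patient to stop drug and remove the patch together. A 4-day overrun then needs an early Visit 6, a late Visit 8 and a late Visit 9, and it needs full adherence, since missed doses stretch the supply. This stands, and it is why the lower frequencies lead here.

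Third, sections 5.4 and 14.3 ask for a check after the first week. A check at 8-11 days meets that, and the share before day 7 is 40% in both periods, with or without the fix. This also stands. What differs in Period 2 is how far a check can stray, not how often it comes early, and no analysis or DSMB rule depends on 5-9 days.

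Fourth, independent uniform windows have no support in the documents. If visits after a late Visit 6 also run late, the 24% shrinks.

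A reader might also infer that the washout becomes too short. The documents do not support that as part of this point. With bottle 1 taken as dispensed, the gap is 33 − 28 = 5 to 37 − 28 = 9 days, and its minimum equals the protocol's own screening rule, "washout lasting a minimum of 5 days" (5.1.1).

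**Conclusion.** The point holds as a low-priority improvement. The extremes (3-11 against 5-9 days; overrun of 4 against 2 days) follow from the documents' windows alone, given that bottle 2 starts at the Visit 6 call and, for the overrun, that the supply is fully taken. The frequencies rest on the assumed uniform, independent windows. The dilution rests in addition on the 40% reduction and an effect that ends with the last capsule. It is about 1.1 points for flecainide given second and 0.6 pooled at worst.

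A reader might infer that the primary result is biased or at risk. The documents do not support that. The order is randomised, so the effect is slight dilution and added variability and does not favour one treatment. The bottle-2 date is recorded, so exposure can be calculated afterwards. Sample size and power are untouched. The absence of a week-4 ICD interrogation in Period 1 is a separate matter that this change leaves as it is.

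**What to change.** In Table 2 and sections 5.1.8 to 5.1.11, count Visits 7, 8, 9 and 10 as 1, 3, 4 and 5 weeks, each within 2 days, after the first bottle-2 dose recorded at Visit 6. The date is already collected, so no new procedure or data field is needed.

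The cost is a wider closeout. Visit 10 would fall on (33 to 37) + 35 ± 2 = days 66-74 instead of 68-72, so participation is at most 2 days longer. The 10-week wording in sections 2.1, 3.2, 5 and 10.3 should then run to Visit 10. In 3.2 this includes the undertaking not to use other antiarrhythmic drugs, so the agreement with patients and physicians should be worded to match.
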